We will include adolescents aged 10 to 16 years. We selected this age range because adolescence is a developmental period of rapid fat gain and changes in activity patterns. By choosing the maximum age as 16 years at baseline, the children are likely to still live in Baton Rouge and attend high school at the second clinic visit (age 18 years), facilitating follow-up.

Inclusion Criteria:

- Age 10-16 years
- Body weight < 500 lbs.
- Ability to understand instructions and complete all study procedures

Exclusion Criteria:

- Pregnant
- On a restrictive diet due to illness
- Significant physical or mental disabilities that impede walking, wearing accelerometer or GPS, or responding to EMA.

In addition to the exclusion criteria listed above, participants who refuse to provide written assent, or whose parents or legally authorized representative refuse to sign an informed consent document, will be excluded from the study. Consent/assent will be obtained upon each participant's arrival at the PBRC Pediatric Research Clinic before participating in any study procedures. To further safeguard participant safety and internal validity of the study, inclusion and exclusion criteria will be reassessed by PBRC clinic staff following the completion of required assent/consent forms. The principal investigator and medical investigator have the right to withdraw a participant from the study at any point for any reason.

Number of Participants

We will identify and recruit up to 345 boys and girls aged 10 to 16 years. The sample will be screened on the telephone in attempt to achieve a comparable sex and race distribution. We will oversample for severely obese youth so they comprise approximately 50% of the sample (with the other 50% being distributed among normal weight, overweight, and obese status).

Recruitment Methods

Recruiting children for clinical studies is challenging, particularly those from high risk populations such as with severe obesity and from ethnic minority groups. However, we are confident we can recruit up to 345 children within 2 years. A key recruitment strategy will be to enroll participants who completed the WAIST Study.¹⁶ Of 423 initial participants who were assessed for the WAIST Study in 2010-11, 386 (91.3%) agreed to be re-contacted. Of these, 193 participants will meet the age criteria for the follow-up

Page 7 of 35

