Participants will be fasting at the Year 0 visit. Measurements including anthropometry, blood draw, urine pregnancy test, body composition, dietary intake, activity monitor tracking equipment collection, and all remaining surveys will take place during the clinic visits. Participants must be accompanied by a parent or legally authorized representative at the clinic visits.

Approximately 10 days prior to the Year 2 visit, participants will pick up an accelerometer and GPS device to wear for 7 days and return at the Year 2 clinic visit. Participants will also be given instructions on how to complete two trials of the ASA-24 dietary intake tool from their home computer prior to the Year 2 clinic visit. Participants will return to clinic approximately 2 years (+/- 6 months) after their Year 0 visit for a Year 2 visit, in which all procedures collected during Year 0 will be repeated. **Table 2** includes a list of all measurements occurring at both visits. Parents may receive reminders from staff for all tasks required of participants between orientation and Year 2.

Measurements

	Orientation	Year 0	Year 2
Informed consent/assent	Х		
Anthropometry (Height, weight, waist size)		Х	Х
Blood Pressure		Х	Х
Body Composition (DXA, MRI)		Х	Х
Blood Draw		Х	Х
Urine Pregnancy Test (eligible females only)		Х	Х
Dietary Intake (ASA-24)		Х	Х
Family environment surveys		Х	Х
Neighborhood environment surveys		Х	Х
Body image and mood surveys		Х	Х
Global Positioning System (GPS)	7-days		7-days
Physical Activity (Actigraph GT3X+)	7-days		7-days
Ecological momentary assessment (eMA)	7-days		

Table 2. Study procedures

Description of tests and procedures

Anthropometry

Weight- Anthropometry will be measured to the nearest 0.1 cm (0.1 kg for weight). All measures are taken twice with the analyzed value being the average of both measurements. If the measures differ by greater than 0.5 units, a third measurement will be taken to replace the discrepant value. Participants wear only a hospital gown and undergarments while being weighed.

Height- Standing height will be measured using a Harpenden stadiometer (Holtain Limited, Crymych, UK). Participants will remove shoes, stand upright with heels and back against the stadiometer, inhale, and hold breath while an assessor provides traction to align the participant's head along the Frankfort Horizontal Plane during measurement. Weight will be measured using a Michelli GSE 460 scale (G.T. Michelli Co., Baton Rouge, LA).

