Participants will complete a survey to collect information about how the participants body weight affects their quality of life, such as physical comfort, body esteem, social life, and family relations.

Resilience Scale (CD-RISC 10)

Participants will complete the 10-item Connor-Davidson Resilience Scale survey to collect information on resilience, which is the ability to thrive despite adversity. The 10-item unidimensional scale has showed excellent psychometric properties including good internal consistency and construct validity.¹¹⁸

Sociodemographics Survey

Parents will report race, ethnicity (i.e. Hispanic), household income, and parental education. These variables will be used as potential covariates in analyses.

Family Environment Survey

Several aspects of the family environment will be measured via parent-reported questionnaire.88,89 The survey we use pertains to children living in a household with parents. The baseline maximum age is 16 years, so we expect all participants to be 18 years and still enrolled in high school at follow-up. However, if any participants no longer live at home, the participant will only complete the physical activity equipment part of this survey. Parents will report the following:

a) physical activity equipment: presence of items at home that facilitate physical activity; internal consistency for this scale has been shown ($\alpha = 0.75$);89

b) family structure: marital status and the number and age of children living in the home;c) household rules: parental rules regarding physical activity;88

d) parent physical activity support: parental support for their child's physical activity over the course of a typical week;88 these four items have been shown to be internally consistent ($\alpha = 0.75$);89

e) parent physical activity behavior: the Aerobics Center Longitudinal Study Physical Activity scale is a self-report measure of current levels of physical activity; this measure asks about various activities and the amount of time spent on each activity, on average and has been shown to be psychometrically sound;90 and

f) sibling physical activity behavior: amount of physical activity for each child over the course of a typical week, including frequency, time, location and type.91

Constrained Behaviors Questionnaire

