Parents will be asked to answer questions regarding their constrained behavior, which are parenting behaviors that restrict their child from outdoor play in their neighborhood (i.e. avoidance and defensive behaviors). This measure was validated by Carver et al., 2010.-¹¹⁹

Neighborhood Impact on Kids (NIK) Survey

Parents (or participant if age is ≥ 18 years) will be asked to report on various aspects of the neighborhood environment, via a questionnaire adapted from the Neighborhood Impact on Kids (NIK) study survey (PI [name], who serves as Consultant on this project),91 which drew on questions from other validated instruments. We have used this questionnaire in other studies.54,95 The questionnaire includes items related to neighborhood social capital (collective efficacy and the degree to which neighbors know each other and engage socially) and the neighborhood physical activity environment and built environment (access to and use of various places where a child can be physically active, and the suitability of the neighborhood environment for walking and physical activity). To measure the child's perception of the neighborhood environment, we will use a short validated survey for the child to report his/her perceptions of access to neighborhood destinations, perceptions of neighborhood aesthetics and safety, and perceptions of the neighborhood social environment.96

Body Image Assessment Procedure for Preadolescents (BIA-P) and Mood and Feelings Questionnaire

The participating child will complete the Body Image Assessment Procedure for Preadolescents (BIA-P),99 which has been demonstrated as reliable and valid in the adolescent age period.99,100 The child will also complete the Short Mood and Feelings Questionnaire (SMFQ), a 13-item scale which has been validated in a community sample of children and adolescents to self-report depressive symptoms.

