Analyses to test the hypotheses will be conducted using linear models. The primary independent variable will be BMIz and the dependent variable will be physical activity (MVPA). The c statistic will be evaluated to assess the contributions of BMIz and the environmental (or socio-emotional) factors to increase the accuracy in model-based prediction of events using data collected at Year 0, Year 2, and the changes between Years 0 and 2. Linear models will also be used to examine if there are changes in environmental or socio-emotional factors between Years 0 and 2. Finally, severe obesity (vs. all others) will be tested as a dichotomous variable with each environmental or socio-emotional factor to determine associations with physical activity. School term vs. school holiday will be considered as an additional covariate if time of year is significantly associated with the independent and dependent variables. For the models investigating environmental factors, the independent variables will include the family environment, park access and crime, perceived neighborhood environment, physical activity locations, and physical activity opportunities. Family environment subscales related to physical activity will initially be summed to create a single continuous score, with higher values indicating higher family support for physical activity. Additionally, the average minutes/day of MVPA will be summarized by location type. To examine socio-emotional factors, the independent variables will include body image, mood, and the data collected from the EMA including the three affect states (i.e. happy, stressed, energetic) and the social context of the activity (i.e. activity type and who was with the participant). For both the environmental and the socio-emotional factors, associations that are positively related to physical activity will be identified as facilitators of each, and inverse associations will be identified as barriers of each.

Contingencies

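### The NIK neighborhood survey changes respondent from parent to participant at age 18, so for the oldest entrants its Year 0 to Year 2 difference mixes true change with a reporting difference

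*Combined protocol and SAP*

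**What the plan says.** All references are to the combined protocol and SAP.

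- **Respondent rule** (Surveys, NIK Survey): "Parents (or participant if age is ≥ 18 years) will be asked to report on various aspects of the neighborhood environment". The same paragraph adds a separate short survey for the child's own perception of the neighborhood, described again under Neighborhood Perception Survey.
- **Entry age** (Inclusion and Exclusion Criteria): "We will include adolescents aged 10 to 16 years". The section explains the upper limit by noting that such children would be 18 at the second visit.
- **Follow-up** (Study Design): "Participants will return to clinic approximately 2 years (+/- 6 months) after their Year 0 visit for a Year 2 visit".
- **Collection**: Table 2 lists "Neighborhood environment surveys" at both Year 0 and Year 2.
- **Analysis** (Statistical Analysis, Objective 3): the environmental factors include "park access and crime, perceived neighborhood environment, physical activity locations, and physical activity opportunities". Data from Year 0, from Year 2 and on the change between them are used, and "Linear models will also be used to examine if there are changes in environmental or socio-emotional factors between Years 0 and 2".
- **Who attends** (Study Design): "Participants must be accompanied by a parent or legally authorized representative at the clinic visits".

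The text reviewed has no rule for NIK pairs answered by different people: no respondent covariate, no exclusion and no sensitivity analysis.

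**The concern.** Nobody is 18 at Year 0, so the age clause can act only between the two visits. It turns some within-family differences into comparisons of two people's views. The protocol itself keeps parent and child views of the neighborhood apart by measuring them on separate forms, so it cannot take them as interchangeable.

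Two uses of the data are exposed. First, a test of whether the neighborhood score changed could pick up a change of reporter. Second, where NIK change is related to physical activity, the switch follows age exactly. If the oldest adolescents also change differently in activity, an association could be created or hidden. Objectives 1 and 2 name age as a covariate. Objective 3 names only school term versus holiday, as an additional covariate. Even a linear age term would not remove a step at 18.

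**Working it through.** **What the difference contains.** Let P0 be the parent's Year 0 score, C2 the participant's Year 2 score, and P2 the score the parent would have given at Year 2. For a switched pair

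C2 − P0 = (P2 − P0) + (C2 − P2).

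The first bracket is the change wanted; the second is the reporting difference. P2 is not collected, so the split cannot be recovered from the NIK data. A respondent indicator does not solve this, because it equals an indicator for age 18 or over at Year 2.

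**Who can switch.** The participant must satisfy baseline age + t ≥ 18, with t between 1.5 and 2.5 years. At t = 2.5 the youngest possible is 18 − 2.5 = 15.5 at baseline, so nobody younger switches within the window. At t = 2.0 everyone who had turned 16 by baseline switches.

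**How many.** The plan gives no figure to reproduce, and no age distribution. Enrolment aims at balance on sex and race and oversamples severe obesity; age is not controlled. The shares below therefore assume evenly spread ages. Returners are 345 × 0.87 = 300, using the 13% non-return under Anticipated Dropout.

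- Age 16 running to the 17th birthday (10.0 to under 17): share = (17 − (18 − t))/7 = (t − 1)/7.
- Maximum of exactly 16.0: share = (t − 2)/6, or 0 if negative.

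| Follow-up t | 10.0 to under 17 | Exactly 16.0 maximum |
|---|---|---|
| 1.5 years | 0.5/7 = 7.1% (21 of 300) | 0% |
| 2.0 years | 1/7 = 14.3% (43 of 300) | 0% |
| 2.5 years | 1.5/7 = 21.4% (64 of 300) | 0.5/6 = 8.3% (25 of 300) |

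Averaged over visits spread evenly across the window, the shares are about 14% and 2%. At the plan's 25% combined dropout, 345 × 0.75 = 259, and 259/7 = 37 switch at 24 months.

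**Sensitivity to the even-age assumption.** Put weights 1 to 7 (sum 28) on the seven single-year ages. At 24 months the share is 1/28 = 3.6% if the sample leans young and 7/28 = 25% if it leans old.

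**Which reading of 16 fits better.** Recruitment Methods counts 193 of 386 re-contactable prior-cohort participants as age-eligible. That cohort was evenly spread over ages 5 to 18, which is 14 single-year ages, and 386 × 7/14 = 193. The match fits an eligible band of seven single-year ages, and so 16 running to the 17th birthday, but does not prove it.

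**Effect on a mean.** The documents give no parent-participant difference. If it were 0.2 to 0.5 SD (assumed), it would enter each switched pair in full. The overall mean change would shift by 0.143 × 0.2 = 0.03 SD to 0.143 × 0.5 = 0.07 SD at 24 months.

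**The case against.** The best counter-argument is that Objective 3 does not name the instrument behind perceived neighborhood environment. The protocol uses the language of perception mainly for the child's own survey, which the child answers at every age. If that survey alone is meant, this variable has no change of respondent. That stands, and it makes the point conditional: it applies to any Objective 3 analysis that uses NIK change. It does not dispose of the point. The neighborhood surveys are collected at both visits, the plan tests change in environmental factors generally, and nothing excludes the NIK.

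It is also fair that the share is unknown and could be close to zero, that the NIK is one input among many, and that park access, crime, GPS locations and facility counts do not depend on a respondent.

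Timing limits the remedy. The protocol version is dated 3/1/2021, recruitment was expected to end in spring 2018, and 30 months later is autumn 2020. The COVID-19 Survey section mentions participants who have already completed Year 2. The documents do not say that all visits are done, but re-routing a form cannot recover parent reports for visits already made.

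Two stronger readings are tempting, and the documents support neither. The Family Environment Survey section says "we expect all participants to be 18 years and still enrolled in high school at follow-up", from which a reader might infer that every pair switches. A child who enters at 10 is at most 12.5 at the latest Year 2 visit under the window if just 10 at entry, so the statement cannot hold for the whole cohort and does not enlarge the share. A reader might also infer that the switched difference carries no information on change. It does carry it, but inseparably from the reporting difference.

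**Conclusion.** The point holds, conditional on the NIK being used in the change analyses. The protocol's own rule makes the NIK difference for participants aged 18 or over at Year 2 a sum of true change and a reporting difference. The rule is confined to the oldest entrants, and the plan has no handling for it.

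The size is not a document figure. About 14% at 24 months, with 7% to 21% over the visit window, rests on evenly spread ages from 10.0 to under 17. If the maximum is exactly 16.0, the range is 0% to about 8%. A reader should not take one child in seven as established.

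The scope is limited. NIK change is affected and, to a lesser extent, so are Year 2 NIK scores that pool respondents. Year 0 models, the child-reported survey, the objective environmental measures and the primary outcomes of Objectives 1 and 2 are not. This should be corrected, but it does not threaten the study's main results.

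**What to change.** 1. State in the Objective 3 analysis which instrument or instruments supply perceived neighborhood environment.
2. For any Year 2 visits still to come, have the parent complete the NIK for every participant still living at home, with self-report at 18 or over as an extra form. A parent or representative already has to attend.
3. Base the main NIK change analysis on pairs with the same respondent. Add a sensitivity analysis that includes the switched pairs, and report how many switched.

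The cost is one extra form at remaining visits, some survey-routing wording and one analysis rule. For visits already completed, the main NIK change analysis loses participants who were 18 or over at Year 2 and answered for themselves. It then applies to younger participants, and the report should say so. The child-reported Neighborhood Perception Survey covers the lost group only in part: its description does not list NIK content such as collective efficacy or the use of places for activity.

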The Personal Experiences Checklist provides a self-report assessment of a young person's personal experience of being bullied. The measure is suitable for both girls and boys aged 8 to 16 years and it covers the full range of bullying behaviors, including covert relational forms of bullying and cyber bullying. There are four subscales: physical, relational, cultural, and cyber.

Food Craving Inventory (FCI)

The food craving survey is a self-reported measurement of how often the participant experiences a craving for listed foods. The survey is 33 items long, and includes various foods and beverages. Participants will indicate on the survey how many cravings he or she has had in the past month.

- White M, et al. Development and validation of the food-craving inventory, Obes Res. 2002;10:107-114.
- Geiselman P et al. *Reliability and validity of a macronutrient self-selection paradigm and a food preference questionnaire*. PHYSIOL BEHAV. 1998; 63(5): 919-928.

Neighborhood Perception Survey

Participants will complete this validated survey to measure the child's perception of his or her neighborhood environment. The self-reported survey indicates the child's perception of access to neighborhood destinations, perceptions of neighborhood aesthetics and safety, and perceptions of neighborhood social environment.

Sibling Relationship Questionnaire (SRQ)

Participants with sibling(s) who are also enrolled in the study will complete a shortened version of the Sibling Relationship Questionnaire (Furman and Buhrmesters 1985) for each sibling in the study. Participants will be asked to gauge the quality of their sibling relationships through questions related to the constructs of prosocial, affection, companionship, similarity, intimacy, admiration of sibling, and admiration by sibling. A psychometric analysis of this questionnaire was examined among a sample of 428 adolescents and confirmed that stated seven constructs form an overall factor of warmth/closeness.

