The hypotheses will be tested using a series of generalized linear models with severe obesity as the independent variable. First, linear mixed effect models will be used to test for effects between BMIz and each dependent continuous variable (change in: min/day sedentary behavior, min/day MVPA, and each cardiometabolic risk factor). Next, logistic regression models will be used to determine the association between BMIz with the likelihood of not meeting recommended behaviors (i.e. top quartile of min/day of sedentary behavior; MVPA < 60 min/day) or being at elevated cardiometabolic risk. Finally, the cohort will be stratified into two groups based on obesity at Year 0: severely obese (SO) and not severely obese (NSO). Logistic regression models will be used to determine associations between SO (vs. NSO) and each dependent variable (i.e. change in: minutes/day sedentary time, minutes/day MVPA, and each continuous cardiometabolic risk factor). Covariates will include age, sex, dietary intake, and race. School

term vs. school holiday will be considered as an additional covariate if time of year is significantly associated with the independent and dependent variables.

Secondary analysis will use MRI and DXA as covariates in the model (namely the visceral, trunk, and total body fat). These measurements, along with BMIz, may be highly correlated. Various variable select criteria (including LASSO and support vector machine) will be used to determine which combination of these variables best explains the variance in the data. The full model will enable the comparison of imaging-based body composition measures vs. BMIz alone and their associations with physical activity, sedentary behavior, and cardiometabolic risk factors in children.

As exploratory analyses, dietary intake will be tested as a potential mediator to explain significant associations between the predictor variable (BMIz) on outcomes (physical activity, sedentary behavior, and cardiometabolic risk factors). Series of sequential models will be used to test each pathway using a path analysis model based on the Baron and Kenny causal steps for mediation.73,74

Objective 2:

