Analyses to test Hypothesis 2 will be conducted using a series of linear regression models (i.e. linear mixed effects models). Based on difference score between Years 0 and 2 for total body fat, the group will be divided into two dichotomous groups using percentiles: high fat gainer (HFG) and low fat gainer (LFG). These variables will be used to predict changes in physical activity, sedentary behavior, and each cardiometabolic risk factor in linear mixed effect models. Covariates will include age, sex, dietary intake, and race. School term vs. school holiday will be considered as an additional covariate if time of year is significantly associated with the independent and dependent variables. Secondary analysis will use MRI and DXA as covariates in the model (namely the visceral, trunk, and total body fat). As previously reported, variable select criteria (including LASSO and support vector machine) will be used to determine which combination of these variables best explains the variance in the data. The full model will enable the comparison the accumulation of imaging-based body composition measures vs. BMIz alone and their associations with change in physical activity, sedentary behavior, and cardiometabolic risk factors in children. Finally, there are no standard accepted definitions of pediatric severe obesity to dichotomize participants based on MRI or DXA measures of body fat. Therefore, receiver operating characteristic curves will be created to estimate the value at which visceral, trunk, and body fat best correspond with the BMI definition of severe obesity (i.e. $BMI \ge 120\%$ of the 95th percentile1). Clinically relevant cut-points of severe obesity based on total, trunk, and visceral body fat will be established among this diverse cohort of adolescents.

Power analysis

Objective 1:

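### Siblings may be enrolled together, but no model names a family term; to the extent siblings resemble each other, standard errors will be too small, chiefly for address-based exposures

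*Combined protocol and SAP*

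**What the plan says.** The SRQ entry under Surveys reads "Participants with sibling(s) who are also enrolled in the study will complete a shortened version" of that questionnaire, and the form is completed "for each sibling in the study". Sets of more than two are therefore possible. The Inclusion and Exclusion Criteria do not restrict enrolment to one child per household.

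The Statistical Analysis section describes the models as follows.

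- **Objective 1.** The opening statement is "The hypotheses will be tested using a series of generalized linear models with severe obesity as the independent variable". For the continuous outcomes: "First, linear mixed effect models will be used to test for effects between BMIz and each dependent continuous variable". For severely obese (SO) against not severely obese (NSO): "Logistic regression models will be used to determine associations between SO (vs. NSO) and each dependent variable". The adjustment set is given as "Covariates will include age, sex, dietary intake, and race", with school term or holiday as a possible addition.
- **Objective 2.** "Analyses to test Hypothesis 2 will be conducted using a series of linear regression models (i.e. linear mixed effects models"), with the same adjustment set.
- **Objective 3.** "Analyses to test the hypotheses will be conducted using linear models". The environmental predictors include family environment, park access, crime and physical activity opportunities.

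None of these names a family or household random effect, GEE, cluster-robust standard errors or a one-child-per-family analysis. The Power analysis section contains no design effect.

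**The concern.** Siblings share parents, home, routines and address, so their activity and its change over two years may well be correlated. A model that counts two such children as two independent observations overstates the information in the data. For a regression coefficient the overstatement depends on the product of the sibling correlation in the outcome and that in the exposure.

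Objective 3 is the most exposed. Neighbourhood is defined by a street-network buffer around the child's residence, or secondarily by Census Block Group. Siblings who live together then have the same values for park access, crime index and facility counts. At stake are the intervals and p-values by which Objective 3 labels a factor a barrier or a facilitator and, to a lesser degree, the SO comparison in Objective 1.

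**Working it through.** **1. The plan's own figure.** Table 5 gives a minimum of 266 for a 24 min/day difference with SD 69.6, alpha 0.05 and 80% power. The usual two-sample formula (two-sided, 1:1) gives 133 per group, or 266 in total, with every child counted as independent. The other rows of Tables 5 and 6 also reproduce to within 3% without a design effect.

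**2. Can the named mixed models absorb sibling correlation?** The Objective 1 and 2 outcomes are change scores, Year 2 minus Year 0, so each child contributes one value. A child-level random effect cannot then be separated from residual error. Only a family-level effect would help, and none is stated.

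**3. Design effect.** Let f be the share of children in sibling pairs, ICCy the sibling correlation of the outcome and ICCx that of the exposure. Then

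DEFF = 1 + f × ICCy × ICCx.

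The true SE is √DEFF times the naive SE, so the naive SE is too small by 1 − 1/√DEFF. The actual type I error is 2 × [1 − Φ(1.96/√DEFF)]. The formula does not depend on the sample size. For logistic models it is an approximation.

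**4. Fully shared exposure (ICCx = 1).** The documents give no f or ICCy; the values below are assumptions.

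| f | ICCy | DEFF | True SE larger by | Naive SE too small by | Type I error |
|---|---|---|---|---|---|
| 0.1 | 0.1 | 1.01 | 0.5% | 0.5% | 5.1% |
| 0.2 | 0.3 | 1.06 | 3.0% | 2.9% | 5.7% |
| 0.4 | 0.3 | 1.12 | 5.8% | 5.5% | 6.4% |
| 0.4 | 0.5 | 1.20 | 9.5% | 8.7% | 7.4% |
| 0.6 | 0.5 | 1.30 | 14.0% | 12.3% | 8.6% |

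**5. Simulation check.** Ordinary least squares with n = 260 and 8,000 replicates, shared exposure, gave type I error of 5.9% (f = 0.2, ICCy = 0.3), 6.0% (0.2, 0.5), 6.5% (0.4, 0.3) and 7.2% (0.4, 0.5). The formula gives 5.7%, 6.2%, 6.4% and 7.4%. With an exposure uncorrelated between siblings, the simulated error was 4.6-5.1%.

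**6. Severe obesity (assumed ICCx = 0.5, f = 0.2-0.6, ICCy = 0.3-0.5).**

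- Low end: DEFF = 1 + 0.2 × 0.3 × 0.5 = 1.03, so the naive SE is 1.5% too small.
- High end: DEFF = 1 + 0.6 × 0.5 × 0.5 = 1.15, so the naive SE is 6.7% too small.

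The 266 becomes 274 (266 × 1.03) to 306 (266 × 1.15). With 345 × 0.75 = 259 analysable children, power for the 24-minute difference is 79.2% if all are independent, and 78.0% to 73.4% over this range.

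**The case against.** The strongest reply is that the SRQ text only says what happens if a sibling is also enrolled. The Recruitment Methods describe reaching individual children through a prior cohort, schools, clinics and advertising, with no family-based recruitment. Siblings may be few, and then the effect is negligible, as the first row of the table shows. This stands. It limits the size of the problem, but the analysis plan still has no provision for siblings.

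Three stronger readings are tempting, and the documents do not support them.

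- A reader might infer that standard errors are certainly too small and false-positive rates certainly above 5%. That needs an appreciable sibling share and positive sibling correlation in both outcome and exposure. The documents give none of these.
- A reader might infer that all family and neighbourhood predictors are identical for siblings. That holds only for address-based measures, and only when siblings share a residence. In the Family Environment Survey, parental support concerns the particular child and sibling activity is recorded child by child, so the summed score can differ within a family. Perceived neighbourhood, GPS locations, body image, mood and EMA responses include measures taken on the individual child.
- A reader might infer that every model ignores family. For the Objective 1 and 2 mixed models the grouping level is simply not stated, so a family effect is not excluded. The omission is plain only for the Objective 3 linear models and the Objective 1 logistic models.

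**Conclusion.** The point holds in conditional form. Sibling enrolment is foreseen and not limited, and the Objective 3 linear and Objective 1 logistic models as written would treat siblings as independent. The mixed models leave the matter open, and a child-level effect would not settle it.

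Over the assumed ranges (f = 0.1-0.6, ICCy = 0.1-0.5), the naive SE for an address-based exposure is about 0.5-12% too small and the type I error about 5.1-8.6%. For severe obesity, under the narrower assumptions shown above, the shortfall is about 1.5-6.7%. The family environment score should also be affected less than a fully shared exposure, and an exposure uncorrelated between siblings hardly at all. Results near the upper end need a large share of siblings in the cohort. The calculation assumes pairs; larger sets would raise the design effect. The change is worth making because the direction is predictable and the remedy is cheap, not because a large error has been shown.

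**What to change.** Derive a household identifier. Staff must already know which siblings are enrolled in order to give them the SRQ, and the data management section describes a master file linking names, addresses and ID numbers. Someone with access to that file can create a coded identifier and pass it to the de-identified analysis dataset.

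Then state in the Statistical Analysis section that all Objective 1-3 models use household-clustered standard errors or GEE, or a family random intercept, and name the random effect wherever a mixed model is kept. Clustered standard errors or GEE are the simpler choice for the logistic models and if sibling sets are few. Report the number and size of sibling sets with the results, so that readers can judge how much the adjustment matters.

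The cost is a sentence or two in the plan and one derived variable, with no new data collection. Intervals become slightly wider, and little changes if siblings are few.
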